6.13. Pharmacokinetic/Pharmacodynamic Methods

More details of the pharmacokinetic/pharmacodynamic (PK/PD) analyses can be found in a separate PK/PD analysis plan.

Briefly, observed ixekizumab serum trough concentrations will be summarized by time point across the study. The PK parameters of ixekizumab in pediatric subjects will be determined using population PK methods. The exposure-response relationship will be investigated between steady-state trough concentrations of ixekizumab and clinically important efficacy measures (for example, sPGA and PASI endpoints) at Week 12 using graphical methods and, if appropriate, modeling methods. If applicable, the potential impact of immunogenicity on ixekizumab exposure and/or exposure or efficacy responses may be evaluated by graphical assessments, as appropriate, to compare drug exposure or efficacy responses between antidrug antibody- (ADA-) negative and ADA-positive subjects at corresponding visits, or before and after ADA development for subjects who developed ADA. Both treatment-emergent only and all ADA-positive/negative subjects may be explored. A similar approach may be taken if subjects become neutralizing antibody positive.

Additional analyses may be performed upon receipt of the data. The data from this study may be combined with data from previous adult studies, if needed, for model development.

6.14. Safety Analyses

Safety will be assessed by summarizing and analyzing AEs, laboratory analytes, including neutrophil counts and immunogenicity; vital signs, CDRS, and C-SSRS. The duration of dosing exposure will also be summarized. Immunization history will be summarized at baseline, and any unexpected outcomes or effects related to standard-of-care vaccination will be summarized.

For Period 2 in Main Protocol RHCD, the safety data will be summarized and analyzed for the safety population with treatment comparisons of ixekizumab versus placebo. This population will be abbreviated as “P2 Main Study Safety Population.”

For Period 2 in Protocol Addendum RHCD(2), the select safety data will be summarized and analyzed for the safety population etanercept-approved countries with all pairwise comparisons. This population will be abbreviated as “P2 Addendum Safety Population.”

For Period 4 in Protocol Addendum RHCD(2), the select safety data will be summarized and analyzed for the Double-Blind, Randomized Withdrawal Period Population with treatment comparisons of ixekizumab versus placebo. This population will be abbreviated as “P4 Randomized Withdrawal Population.”

For all ixekizumab treatment periods combined (Period 2, 3, and 4), the safety data will be summarized to all ixekizumab population. This population will be abbreviated as “All Ixekizumab Safety Population.”

For Period 5, safety data will be summarized using Follow-Up Population.

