5.1. Overall Design

- **Period 4:**

Extension Period will occur from Week 60 (Visit 19) to Week 108 (Visit 31). Subjects from countries outside of the EU, irrespective of response, and nonresponders from the EU will continue with open-label treatment with the ixekizumab dose received during the previous period.

OR

48-Week Double-Blind, Randomized Withdrawal Period will occur from Week 60 (Visit 19) to Week 108 (Visit 31) for subjects in the EU who meet the response criterion at Week 60 (defined as sPGA [0,1]). Subjects will be rerandomized to ixekizumab or placebo (1:1 ratio).

5.1.4. **48-Week Extension Period or Double-Blind, Randomized Withdrawal Period (Period 4)**

Subjects from EU countries who meet the response criterion at Week 60 (defined as sPGA [0,1]) will be rerandomized to ixekizumab or placebo (1:1 ratio) at Visit 19 (Week 60). Subjects who

are rerandomized to ixekizumab will receive ixekizumab 20, 40, or 80 mg every 4 weeks (Q4W) according to their weight at the time of rerandomization. Upon disease relapse to Ps (sPGA \geq 2), subjects will receive ixekizumab 20, 40, or 80 mg Q4W according to their weight. Subjects from EU countries who do not meet the response criterion at Week 60 will continue with open-label treatment with ixekizumab.

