10.3.1. General Statistical Considerations

During the Double-Blind, Randomized Withdrawal Period (Period 4), approximately 40 subjects from EU countries will be rerandomized to ixekizumab (20 subjects) and placebo (20 subjects) in a 1:1 ratio. The response criterion for rerandomization is sPGA (0,1) at Week 60.

The study will have approximately 95% power to test the superiority of ixekizumab to placebo in time to relapse (sPGA \geq 2) based on the 2-sided log-rank test at a significance level of 0.05. The following assumptions were used for the power calculations: 20% relapse for ixekizumab and 85% relapse for placebo. Relapse rates were estimated based on ixekizumab clinical studies in adult subjects with moderate-to-severe Ps efficacy data (Griffiths et al. 2015; Gordon et al. 2016).

Unless otherwise specified, efficacy, health outcomes, and safety analyses for the Double-Blind, Randomized Withdrawal Period will be conducted on the Double-Blind, Randomized Withdrawal Period Population, defined as all rerandomized patients (i.e., subjects from countries in the EU who were rerandomized at Week 60) who received at least 1 dose of study treatment during Double-Blind, Randomized Withdrawal Period. Patients will be analyzed according to the treatment to which they were rerandomized.

Treatment comparisons of ixekizumab and placebo during the Double-Blind, Randomized Withdrawal Period will be performed for the Double-Blind, Randomized Withdrawal Period Population.

The time to relapse (loss of response; sPGA ≥ 2) during Double-Blind, Randomized Withdrawal Period (Period 4) is defined as:

$$\textit{Time to relapse (days)} = \textit{date of first sPGA} \geq 2 \textit{ during Period 4} - \textit{date of Week 60 rerandomization} + 1.$$

If a patient has not experienced relapse (sPGA ≥ 2) by completion or early discontinuation of Period 4, the patient will be censored at the date of their last visit during Period 4.

The number of patients at risk and experiencing a relapse event by each scheduled visit during Period 4 will be presented by treatment group. The Kaplan–Meier estimate of the proportion of patients relapsing will be presented for each visit. Treatment group comparisons will be performed using the log-rank test. For each treatment group, a Kaplan–Meier plot of the time to relapse will be provided.

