5.3.2. Protocol Addendum RHCD(2)

Subjects from countries where etanercept is approved for severe pediatric Ps treatment only who meet all criteria for enrollment at Visit 1 and Visit 2 will be randomized to double-blind treatment at Week 0 (Visit 2) in a 2:2:1 ratio to ixekizumab, etanercept, or placebo.

Subjects who meet response criteria (sPGA 0,1) from EU countries will enter the Double-Blind Randomized Withdrawal Period and will be re-randomized to double-blind treatment at Week 60 (Visit 19) in a 1:1 ratio to ixekizumab or placebo. Subjects who are re-randomized to ixekizumab will receive ixekizumab 20, 40, or 80 mg every 4 weeks (Q4W) according to their weight at the time of re-randomization. Subjects from EU countries who relapse (sPGA ≥ 2) during the Double-Blind Randomized Withdrawal Period will receive open-label treatment with ixekizumab according to their weight at the time of relapse.

6. A Priori Statistical Methods

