6.14.1. Extent of Exposure

Duration of exposure to study drug will be summarized by treatment group using descriptive statistics, the summary will also include the total exposure in patient years, mean, and median total dose. Exposure of the following safety population will be summarized:

- P2 Main Study Safety Population
- P2 Addendum Safety Population
- P4 Randomized Withdrawal Population
- All Ixekizumab Safety Population

The duration of exposure will be calculated as:

- *Duration of exposure (days) =*
Date of last visit (scheduled or unscheduled) in the treatment period –
Date of first dose in the treatment period + 1

- Total exposure in patient years will be calculated as:

$$\text{Total exposure in patient years} = \frac{\text{Sum of duration (days) of exposures for all patients in treatment group}}{365.25}$$

- Total dose (in mg) is calculated by the summation of dose for each active injection taken during the treatment period. Dose for placebo injection will be 0.

For P2 Main Study and P2 Addendum Safety Populations, the number and percentage of patients in each of the following categories will be included in the summaries:

- >0, ≥7 days, ≥14 days, ≥30 days, ≥60 days, ≥84 days, and ≥90 days. Note that patients may be included in more than 1 category.
- >0 to <7 days, ≥7 to <14 days, ≥14 to <30 days, ≥30 to <60 days, ≥60 to <84 days, ≥84 to <90 days, and ≥90 days.

For P4 Randomized Withdrawal Population, the number and percentage of patients in each of the following categories will be included in the summaries:

- >0, ≥7 days, ≥14 days, ≥30 days, ≥60 days, ≥84 days, ≥90 days, ≥120 days, ≥183 days, and ≥365 days. Note that patients may be included in more than 1 category.
- >0 to <7 days, ≥7 to <14 days, ≥14 to <30 days, ≥30 to <60 days, ≥60 to <84 days, ≥84 to <90 days, ≥90 to <120 days, ≥120 to <183 days, ≥183 to <365 days, and ≥365 days

For the All Ixekizumab Safety Population, duration of exposure for each uninterrupted ixekizumab treatment period will be calculated as:

$$\begin{aligned} \text{Duration of ixekizumab exposure (days)} \\ &= \text{Date of last visit of ixekizumab treatment period} \\ &\quad - \text{Date of first dose of ixekizumab treatment period} + 1 \end{aligned}$$

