6.14.2. Adverse Events

Adverse events will be classified based upon the latest version of the MedDRA. Adverse events will be recorded at every study visit. Any condition starting on or after the date of informed consent will be considered an AE. Any preexisting condition which worsens in severity on or after the date of informed consent will be considered and recorded as an AE on the Adverse Event (AE) eCRF page from the date of worsening onward.

A treatment-emergent adverse event (TEAE) is defined as an event that first occurred or worsened in severity after baseline and on or prior to the date of the last visit within the defined treatment period. Both the date/time of the event and the date/time of the dose (that is, injection) are considered when determining TEAEs. Treatment-emergent AEs will be assigned to the study period to which it is considered treatment-emergent:

- The MedDRA lowest level term (LLT) will be used when classifying AEs as treatment-emergent.
- The maximum severity recorded for each LLT prior to the first dose date/time in the treatment period will be used as the pre-treatment severity for that LLT. If an event during the baseline period has missing severity, and the event persists during the treatment period, then it will be considered as treatment-emergent, regardless of the postbaseline level of severity. Events with a missing severity during the treatment period will be considered treatment-emergent.
- AEs with a particular LLT will be classified as treatment-emergent if they first start on or after the first dose date/time in the treatment period (that is, a patient has no preexisting conditions with that LLT), or if the severity is greater than the pre-treatment severity for that LLT. If a partial AE start date/time is present, the date/time will be compared as far as possible to the treatment start date/time in order to determine whether the event is treatment-emergent. If there is any doubt, the event will be flagged as treatment-emergent.

A follow-up-emergent adverse event (FEAE) is defined as an event that first occurred or worsened in severity after the date of Visit 31 (that is, Week 108) or the ETV:

- The MedDRA LLT will be used when classifying AEs as follow-up-emergent.
- For AEs that are ongoing at the date of Visit 31 or ETV, the maximum severity recorded for each LLT on or prior to the date of Visit 31 or ETV will be used as the follow-up baseline severity for that LLT.

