In general, for all AE-related summaries, the number and percentage of patients experiencing the events will be presented by treatment group. In general, events will be ordered by decreasing frequency in the total ixekizumab group, followed in the order of ixekizumab Q4W, etanercept, and placebo (when applicable) group, within SOC and/or PT for sorting. For events that are gender-specific (as defined by MedDRA), the denominator and computation of the percentage will include only patients from the given gender.

A by-patient listing of all AEs will be provided.

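### The Period 4 safety tables have no cut-off at rescue, so open-label ixekizumab time, dose and events in relapsed placebo subjects are reported under placebo

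*SAP*

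**What the plan says.** Five rules combine.

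- **Length of the period.** Protocol Section 5.1 (withdrawal period): "Randomized Withdrawal Period will occur from Week 60 (Visit 19) to Week 108 (Visit 31"). It does not close at relapse.
- **Treatment after relapse.** SAP Section 5.3.2: EU subjects who relapse during the period "will receive open-label treatment with ixekizumab according to their weight at the time of relapse". Protocol Section 7.2 says the same.
- **Attribution.** Protocol Section 10.3.1 applies the withdrawal-period population to safety as well as efficacy: "Patients will be analyzed according to the treatment to which they were rerandomized". SAP Section 6.14 states that "the select safety data will be summarized and analyzed for the Double-Blind, Randomized Withdrawal Period Population with treatment comparisons of ixekizumab versus placebo". SAP Table RHCD.6.2 lists only two Period 4 groups, ixekizumab and placebo.
- **Exposure and dose.** SAP Section 6.14.1 names the Period 4 population among those summarized. Duration ends at the "Date of last visit (scheduled or unscheduled) in the treatment period". Total dose is the "summation of dose for each active injection taken during the treatment period", and only placebo injections count as zero.
- **Adverse events.** Under SAP Section 6.14.2 an event is treatment-emergent if it arises after baseline and "on or prior to the date of the last visit within the defined treatment period". In the tables, "the number and percentage of patients experiencing the events will be presented by treatment group".

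The SAP does separate time before and after rescue in Section 6.1.2 (baseline) and Section 6.14.1 (sum of two ixekizumab exposures). Both rules serve the All Ixekizumab Safety Population only.

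**The concern.** A subject rerandomized to placebo who relapses at, say, Week 76 spends the remaining 32 weeks to Week 108 on ixekizumab. Under the rules above, that time counts as placebo exposure, the ixekizumab milligrams count toward the placebo group's total dose, and any event after rescue counts as a placebo event. The same event is also counted under ixekizumab in the combined-period tables.

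Subjects initially on placebo move to ixekizumab at Week 12, so Period 4 is the trial's only placebo-controlled safety comparison after that point. The plan itself expects most placebo subjects to relapse, so the mixing would be the usual case in that arm. It overstates placebo exposure and tends to hide any difference between the arms. The ixekizumab arm does not have this problem, because its relapsers stay on the same drug.

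**Working it through.** **Inputs.** 20 subjects per arm, and relapse of 20% on ixekizumab and 85% on placebo (SAP 5.2.2). Period 4 lasts Week 60 to Week 108, i.e. 48 weeks or 336 days, with 4-weekly visits (protocol Schedule of Activities). Dropout is set to zero. The timing of relapse is not in the documents and is varied below.

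**The plan's own figure.** The stated power of about 95% reproduces, which confirms that 85% is the planning value:
- Hazard ratio = ln(0.80)/ln(0.15) = 0.1176.
- Events = 20 × 0.20 + 20 × 0.85 = 21.
- Freedman: √21 × (1 − 0.1176)/(1 + 0.1176) − 1.96 = 3.618 − 1.96 = 1.658, giving 95.1%.

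**Nominal placebo time.** 20 × 336/365.25 = 18.40 patient-years.

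**Time before rescue.** Let S(t) be the proportion not yet relapsed, with S(48) = 0.15.
- Rescue at the moment of relapse: mean weeks = ∫ S(t) dt from 0 to 48.
- Relapse found at the next 4-weekly visit: mean weeks = Σ 4·S(4j), j = 0 to 11.

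For example, constant hazard gives 0.85 × 48/1.897 = 21.5 weeks, and uniform timing gives 0.15 × 48 + 0.85 × 24 = 27.6 weeks. The share on ixekizumab is 1 − mean/48. Placebo patient-years are 20 × mean × 7/365.25.

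| Relapse timing (assumed) | Mean weeks before rescue (immediate / next visit) | Share on ixekizumab | Actual placebo patient-years |
|---|---|---|---|
| Constant hazard | 21.5 / 23.3 | 55.2% / 51.6% | 8.24 / 8.91 |
| Uniform | 27.6 / 29.3 | 42.5% / 39.0% | 10.58 / 11.23 |
| Weibull, shape 2 | 29.3 / 31.0 | 39.0% / 35.5% | 11.23 / 11.87 |
| Weibull, shape 3 | 33.6 / 35.3 | 30.0% / 26.5% | 12.89 / 13.53 |

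Ixekizumab time labelled placebo is therefore 18.40 − 13.53 = 4.9 to 18.40 − 8.24 = 10.2 patient-years.

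These patterns are not bounds. If every relapse fell on one day, the mean time before rescue would be 0.85 × 56 + 0.15 × 336 = 98 days for day 56 (share 71%) and 0.85 × 252 + 0.15 × 336 = 264.6 days for day 252 (share 21%).

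**Dose.** There are 12 dosing visits, Week 60 to Week 104. A subject rescued at the k-th visit after rerandomization receives 12 − k active injections. With relapse found at visits, the mean is 6.2 per placebo subject (about 124 in the arm) under constant hazard and 4.7 (about 94) under uniform timing. About 16 of the 20 subjects would have at least one.

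**Illustrative dilution of a rate ratio.** If ixekizumab truly doubled an event rate and the rate changed immediately with treatment, the as-labelled ratio would be 2/(1 + f), where f is the share on ixekizumab: 2/1.552 = 1.29 at the top of the tabulated range and 2/1.265 = 1.58 at the bottom. The planned tables compare percentages of patients, so this shows direction and rough scale only.

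**Formal testing.** With 20 versus 20, Fisher's exact test gives p = 0.106 for 4 versus 0 and p = 0.047 for 5 versus 0.

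**The case against.** **The SAP never says outright that post-rescue data go under placebo.** The treatment period is not defined for a rescued subject, the as-rerandomized sentence is in the protocol rather than in the SAP's definition of this population, and elsewhere the SAP speaks of separate exposure periods. It is true that the result is derived rather than stated. But nothing ends the period at rescue for this population, and the protocol fixes Week 108. If the period did end at rescue, post-rescue data would have no column. The SAP needs a change on either reading.

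**As-rerandomized analysis is a legitimate, prespecified choice.** It keeps the randomized comparison and equal planned follow-up. Cutting placebo at relapse cuts on an outcome, lowers placebo percentages through shorter observation, and gives unstable rates on 8 to 14 patient-years. All of this stands, and it is why the as-rerandomized table should be kept. It does not justify having that table alone, without a label, or showing ixekizumab milligrams under placebo.

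**Pre-rescue time is not ixekizumab-naive.** Every rerandomized subject received ixekizumab in Period 3. This stands: a cut-off gives cleaner withdrawal time, not a naive placebo group.

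**The impact is limited.** Period 4 safety is confined to selected tables, special-interest event tables are not planned for it, by-patient listings exist, and the rescue exposure is handled properly in the All Ixekizumab Safety Population. This also stands and limits the weight of the point. Those combined-period summaries have no control group, however, so they do not repair the Period 4 comparison.

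**Conclusion.** The concern holds. Applied as written, the rules put rescue exposure, ixekizumab dose and post-rescue events in the Period 4 placebo column. Under the tabulated patterns, 26% to 55% of nominal placebo time (4.9 to 10.2 of 18.4 patient-years) would be on ixekizumab, leaving 8.2 to 13.5 patient-years of actual placebo time. This rests on 85% relapse, 20 subjects, no dropout and assumed relapse timing. The attribution error itself depends on none of these; only its size does.

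The distortion in the adverse-event percentages cannot be fixed from the documents. The consequence is mainly descriptive: exposure and dose are misdescribed and the only longer-term controlled safety comparison is blurred. Time to relapse, for which relapse is the event, and the primary and gated Period 2 endpoints are not touched. It should be corrected, but it does not threaten the trial's main conclusions.

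**What to change.** The change is to analysis only; nothing in treatment or rescue is altered.

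1. In SAP Sections 6.14.1, 6.14.2, 6.14.3 and 6.14.4, for subjects rerandomized to placebo in the P4 Randomized Withdrawal Population, end the exposure, total-dose, TEAE, SAE and laboratory windows at the first open-label ixekizumab dose, or at the last Period 4 visit if there is none.
2. Report post-rescue exposure and events in a separate placebo-to-ixekizumab column. The post-rescue baseline rule in Section 6.1.2 can be reused.
3. Do not truncate the ixekizumab arm in this on-treatment summary.
4. Add rates per patient-year, because follow-up would be about 18.4 versus 8.2 to 13.5 patient-years.
5. Keep the as-rerandomized Fisher comparison, labelled as including rescue ixekizumab.

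The cost is a few sentences of SAP text, one derived cut-off date, one extra column and exposure-adjusted rates in the Period 4 outputs. The drawback is that the on-treatment summary stops at an outcome and is no longer a purely randomized comparison; item 5 covers that.

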6.14.1. Extent of Exposure

Duration of exposure to study drug will be summarized by treatment group using descriptive statistics, the summary will also include the total exposure in patient years, mean, and median total dose. Exposure of the following safety population will be summarized:

- P2 Main Study Safety Population
- P2 Addendum Safety Population
- P4 Randomized Withdrawal Population
- All Ixekizumab Safety Population

The duration of exposure will be calculated as:

- *Duration of exposure (days) =*
Date of last visit (scheduled or unscheduled) in the treatment period –
Date of first dose in the treatment period + 1

- Total exposure in patient years will be calculated as:

$$\text{Total exposure in patient years} = \frac{\text{Sum of duration (days) of exposures for all patients in treatment group}}{365.25}$$

- Total dose (in mg) is calculated by the summation of dose for each active injection taken during the treatment period. Dose for placebo injection will be 0.

For P2 Main Study and P2 Addendum Safety Populations, the number and percentage of patients in each of the following categories will be included in the summaries:

- >0, ≥7 days, ≥14 days, ≥30 days, ≥60 days, ≥84 days, and ≥90 days. Note that patients may be included in more than 1 category.
- >0 to <7 days, ≥7 to <14 days, ≥14 to <30 days, ≥30 to <60 days, ≥60 to <84 days, ≥84 to <90 days, and ≥90 days.

For P4 Randomized Withdrawal Population, the number and percentage of patients in each of the following categories will be included in the summaries:

- >0, ≥7 days, ≥14 days, ≥30 days, ≥60 days, ≥84 days, ≥90 days, ≥120 days, ≥183 days, and ≥365 days. Note that patients may be included in more than 1 category.
- >0 to <7 days, ≥7 to <14 days, ≥14 to <30 days, ≥30 to <60 days, ≥60 to <84 days, ≥84 to <90 days, ≥90 to <120 days, ≥120 to <183 days, ≥183 to <365 days, and ≥365 days

For the All Ixekizumab Safety Population, duration of exposure for each uninterrupted ixekizumab treatment period will be calculated as:

$$\begin{aligned} \text{Duration of ixekizumab exposure (days)} \\ &= \text{Date of last visit of ixekizumab treatment period} \\ &\quad - \text{Date of first dose of ixekizumab treatment period} + 1 \end{aligned}$$

If a patient had more than 1 uninterrupted ixekizumab treatment periods, patients who re-randomized to placebo during the Double-Blind, Randomized Withdrawal Period (Period 4) and relapsed, the duration of total ixekizumab exposure is the sum of durations of both uninterrupted ixekizumab exposure.

The number and percentage of patients in each of the following categories will be included in the summaries for the All Ixekizumab Safety Population:

- >0, ≥7 days, ≥14 days, ≥30 days, ≥60 days, ≥84 days, ≥90 days, ≥120 days, ≥183 days, ≥365 days, ≥548 days, and ≥730 days. Note that patients may be included in more than 1 category.
- >0 to <7 days, ≥7 to <14 days, ≥14 to <30 days, ≥30 to <60 days, ≥60 to <84 days, ≥84 to <90 days, ≥90 to <120 days, ≥120 to <183 days, ≥183 to <365 days, ≥365 days to <548 days, ≥548 days to <730 days, and ≥730 days.

